5.5.2. Estimand

Not applicable

5.5.3. Analysis Methods

Formal non-inferiority hypothesis testing will be performed on either the NI set (Scenario 1) or on the PPI set (Scenario 2) as described in Section 4.

Descriptive non-inferiority and additional immunogenicity assessments may be performed on other populations and subgroups (e.g., PPI, or on participants in the PPI who are SARS-CoV-2 seropositive at baseline, etc.).

Immunogenicity analyses may also be done on the FAS (participants who became infected during the study will be analyzed as a subgroup and will be shown in the graphs using different colors

and symbols). Samples taken outside of the allowed windows as described in section 5.1.3 (included in the FAS analysis and excluded from the output in the analysis on PPI) will be included and flagged in the listings as results not included in the PPI analyses.

Key immunogenicity subgroup analyses will also be performed by age group, sex, BMI, race, ethnicity, and serostatus at baseline, as defined in Section 5.1.5.

Categorical variables will be summarized with a frequency table showing counts and percentages.

Continuous variables will be summarized using the following statistics, as appropriate: number of observations, geometric mean, arithmetic mean (mean), 95% confidence interval (CI) for the mean, standard deviation (SD), standard error (SE), median, quartiles (Q1 and Q3), minimum and maximum.

Data listings, participant profiles and/or participant narratives may be provided as appropriate.

Binary variables will be summarized using the following statistics: number of observations, percentages, and Exact Clopper-Pearson 95% CIs.

Formal NI testing will be applied to demonstrate NI of 1-dose and 2-doses of 9×10^{10} vp, 7×10^{10} vp, 3.5×10^{10} vp, 2.5×10^{10} vp and 1.25×10^{10} vp Ad26.COV2.S versus 1-dose and 2-doses of 5×10^{10} vp Ad26.COV2.S (release titer), using a NI margin of 2/3 for the GMC ratios.

The following 2 sets of hypotheses (1 dose and 2 doses) will independently be tested sequentially:

Post-dose 1

1a) NI after 1-dose of Ad26.COV2.S 9×10^{10} vp versus 1-dose of Ad26.COV2.S 5×10^{10} vp (release titer)

1b) NI after 1-dose of Ad26.COV2.S 2.5×10^{10} vp versus 1-dose of Ad26.COV2.S 5×10^{10} vp (release titer)

1c) NI after 1-dose of Ad26.COV2.S 7×10^{10} vp versus 1-dose of Ad26.COV2.S 5×10^{10} vp (release titer)

1d) NI after 1-dose of Ad26.COV2.S 3.5×10^{10} vp versus 1-dose of Ad26.COV2.S 5×10^{10} vp (release titer)

1e) NI after 1-dose of Ad26.COV2.S 1.25×10^{10} vp versus 1-dose of Ad26.COV2.S 5×10^{10} vp (release titer)

In this set, NI will be demonstrated in terms of humoral immune response expressed by the GMCs of S-ELISA, 28 days post-dose 1, using a NI margin of 2/3 for the GMC ratio (GMC [9×10^{10} vp, 7×10^{10} vp, 3.5×10^{10} vp, 2.5×10^{10} or 1.25×10^{10} vp]/GMC 5×10^{10} vp).

Post-dose 2

2a1) NI after 2-doses of Ad26.COV2.S 9×10^{10} vp versus 1-dose of Ad26.COV2.S 5×10^{10} vp (release titer)

2a2) NI after 2-doses of Ad26.COV2.S 9×10^{10} vp versus 2-doses of Ad26.COV2.S 5×10^{10} vp (release titer)

2b1) NI after 2-doses of Ad26.COVID-19 2.5×10^{10} vp versus 1-dose of Ad26.COVID-19 5×10^{10} vp (release titer)

2b2) NI after 2-doses of Ad26.COVID-19 2.5×10^{10} vp versus 2-doses of Ad26.COVID-19 5×10^{10} vp (release titer)

2c1) NI after 2-doses of Ad26.COVID-19 7×10^{10} vp versus 1-dose of Ad26.COVID-19 5×10^{10} vp (release titer)

2c2) NI after 2-doses of Ad26.COVID-19 7×10^{10} vp versus 2-doses of Ad26.COVID-19 5×10^{10} vp (release titer)

2d1) NI after 2-doses of Ad26.COVID-19 3.5×10^{10} vp versus 1-dose of Ad26.COVID-19 5×10^{10} vp (release titer)

2d2) NI after 2-doses of Ad26.COVID-19 3.5×10^{10} vp versus 2-doses of Ad26.COVID-19 5×10^{10} vp (release titer)

2e1) NI after 2-doses of Ad26.COVID-19 1.25×10^{10} vp versus 1-dose of Ad26.COVID-19 5×10^{10} vp (release titer)

2e2) NI after 2-doses of Ad26.COVID-19 1.25×10^{10} vp versus 2-doses of Ad26.COVID-19 5×10^{10} vp (release titer)

In this set, NI will be demonstrated in terms of humoral immune response expressed by the GMCs of S-ELISA, 14 days post-dose 2 (9×10^{10} vp, 7×10^{10} vp, 3.5×10^{10} vp, 2.5×10^{10} vp or 1.25×10^{10} vp) and 28 days post-dose 1 or 14 days post-dose 2 (5×10^{10} vp), using a NI margin of 2/3 for the GMC ratio (GMC [9×10^{10} vp, 2.5×10^{10} , 7×10^{10} vp, 3.5×10^{10} vp, or 1.25×10^{10} vp]/GMC 5×10^{10} vp)

5.5.3.1. Non-Inferiority Analysis- Immune Response

Formal NI testing will be applied to demonstrate non-inferiority of immunogenicity. Non-inferiority will be analyzed by vaccine dose levels. As described in section 4, only one of the two scenarios will be considered for non-inferiority hypothesis testing at primary analysis. If there is an overall loss of $> 40\%$ evaluable data points in the NI set at Day 29 (defined as number of evaluable participants in the NI set at D29/total number of subjects in Table 4), the population in scenario 2 will be used for primary analysis.

- **Scenario 1 (base case scenario):** non-inferiority will be performed on the NI set including participants from the main and the sub study. A linear regression analysis with only one main effect (dose level) will be fitted, with log-transformed (\log_{10} scale) SARS-CoV-2 S-protein specific antibody concentration (S-ELISA) as the response variable and dose level as the independent variable.
- **Scenario 2:** Non-inferiority will be performed on the PPI set including participants from the main study and sub-study. A linear regression analysis with two main effects (dose level and SARS-CoV-2 serostatus at baseline) will be fitted, with log-transformed (\log_{10} scale) SARS-CoV-2 S-protein specific antibody concentration (S-ELISA) as the response variable and dose level and SARS-CoV-2 serostatus at baseline as the independent variables.

Participants with missing serostatus at baseline will not be included in this analysis.

Level of Significance

For each of the 1-dose and 2-dose vaccine regimens hypothesis, the type I error rate α will be set to 0.0125 (1-sided) and non-inferiority (NI) tests will be confirmed by constructing the corresponding 97.5% confidence interval (2-sided) which is equivalent to using $\alpha = 0.025$ (1-sided) with 98.75 (1-sided CI).

Multiplicity Adjustment

The family-wise error rate (FWER) at $\alpha = 0.025$ (one-sided), will be controlled by:

Splitting the Type I error rate $\alpha = 0.025$ into two (i.e., $\alpha = 0.0125$) using Bonferroni correction for the independently tested 1 and 2 doses NI hypotheses (see

[Figure 1](#)).

[Figure 1](#) depicts a tree-based schema for testing the non-inferiority hypotheses controlling the family-wise error rate (FWER) at $\alpha = 0.025$ (one-sided). Non-inferiority of immunogenicity will be assessed by first constructing the 2-sided $(1 - \alpha) \%$ confidence interval for the difference in means based on the sampling distribution of two independent normal distributions with variances that are unknown but assumed equal.

Let $X_g = \log_{10} Y_g \sim N(\mu_g, \sigma_g)$, normally distributed with true population mean and standard deviation, μ_g and σ_g respectively and where X_g is the log-transformed (\log_{10} scale) SARS-CoV-2 S-protein specific antibody concentration (ELISA) data for vaccine dose levels, $\mathbf{g} = \mathbf{A}, \mathbf{B}, \mathbf{C}, \mathbf{D}, \mathbf{E}$ in each hypothesis test (so defined to reflect the hypotheses in

[Figure 1](#) in section 1.3),

Where, $A = 9 \times 10^{10}$ vp; $B = 2.5 \times 10^{10}$ vp; $C = 3.5 \times 10^{10}$ vp; $D = 7 \times 10^{10}$ vp; $E = 1.25 \times 10^{10}$ vp

Let $X_r = \log_{10} Y_r \sim N(\mu_r, \sigma_r)$, where X_r is the log-transformed (\log_{10} scale) SARS-CoV-2 S-protein specific antibody concentration (S-ELISA) data for vaccine dose level 5×10^{10} vp (release titer), the reference dose level, r.

It can be shown that the log-transformed (\log_{10} scale) SARS-CoV-2 S-protein specific antibody concentration (S-ELISA) mean differences between the vaccine dose levels g , $(\bar{X}_g - \bar{X}_r)$, is equal to the log-transformed (\log_{10} scale) ratio of the corresponding geometric means, i.e., $\log_{10}(GMC_g/GMC_r)$

Hence, back transforming yields, $GMC_g/GMC_r = 10^{(\bar{X}_g - \bar{X}_r)}$ as the geometric mean ratio estimates.

Next, we can construct the $(1 - \alpha) \%$ confidence interval (2-sided) for the geometric mean ratios, by first constructing the confidence interval on the difference on the means, $(\bar{X}_g - \bar{X}_r)$.

Assuming unknown equal variances for the population vaccine dose levels g and release titer, reference dose level, r , and log-transformed (log₁₀ scale) SARS-CoV-2 S-protein specific antibody concentration (S-ELISA, the $(1 - \alpha)$ % confidence interval (2-sided) estimate for the population vaccine dose level g and reference dose level r mean differences, is given by,

$$(\bar{X}_g - \bar{X}_r) \pm t_{(1-\alpha/2; v_p)} S_p \sqrt{\left(\frac{1}{n_g} + \frac{1}{n_r}\right)}$$

Where the pooled variance estimate, $S_p^2 = \frac{(n_g-1)s_g^2 + (n_r-1)s_r^2}{n_g+n_r-2}$ and $v_p = n_g + n_r - 2$ is the degrees of freedom for the t-distribution and $\alpha = 0.0125$.

Since log transformation is monotone, back transforming confidence intervals for the difference in means in the log scale gives a confidence interval for the ratio of the geometric means. Hence, the lower and upper bounds of the 2-sided $(1 - \alpha)\%$ confidence interval for the GMC ratios are as follows:

$$\begin{aligned} ((GMC\ Ratio))_{Lower\ Bound} &= 10^{\left(\bar{X}_g - \bar{X}_r - t_{(1-\alpha/2; v_p)} S_p \sqrt{\left(\frac{1}{n_g} + \frac{1}{n_r}\right)}\right)} \\ ((GMC\ Ratio))_{Upper\ Bound} &= 10^{\left(\bar{X}_g - \bar{X}_r + t_{(1-\alpha/2; v_p)} S_p \sqrt{\left(\frac{1}{n_g} + \frac{1}{n_r}\right)}\right)} \end{aligned}$$

For each of the vaccine dose level, g comparisons (post-dose 1 and post-dose 2), NI will be demonstrated if

$$((GMC\ Ratio))_{Lower\ Bound} > \frac{2}{3}$$

If the assumptions of the unknown equal variances for the independent normal distributions of vaccine dose levels do not hold (i.e., test of equality variances shows that the variances are significantly different), then an approximate t-distribution with Satterthwaite approximated degrees of freedom will be used instead of (6) (Casella, G & Berger L.R (1990)).

SAS v 9.4 will be used in implementing the above NI comparisons.

Remarks:

No generally accepted immunological correlate of protection has been demonstrated for SARS-CoV-2 to date. If a correlate or threshold for protection against COVID-19 is established in terms of humoral immunity, then a statistical comparison to that correlate or threshold will be performed in addition, as outlined in a revised analytical plan. If the correlate or threshold of protection will be used as an endpoint the definition of seroconversion and seroconversion rate will be described in Section 5.7.

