9.2. Sample Size Determination

The number of participants chosen is to provide sufficient power for the non-inferiority comparisons stated in Section 9.1.

The following assumptions were made in the sample size determinations:

- Log transformed (log10 scale) immune response data are normally distributed
- A common standard deviation (SD): SD 0.5 (log10 scale) of the immune response log transformed data
- Non-inferiority margin $\log_{10}(2/3) = -0.176$

- Alpha 0.025 (one-sided). Using a Bonferroni correction, Type I error will be split equally over the 1-dose and 2-dose comparisons: 0.0125 (1-sided) for 1- and 2-dose NI comparisons
- Power 90%

Based on the above assumptions, assuming approximately a 10.2% dropout, a sample size of 225 participants per active vaccine group (see [Table 1](#)) is needed to detect non-inferiority of testing 1-dose and 2-doses of 9×10^{10} vp, 2.5×10^{10} vp, 7×10^{10} vp, 3.5×10^{10} vp, and 1.25×10^{10} vp Ad26.COV2.S as the test groups versus 1-dose and 2-doses of 5×10^{10} vp Ad26.COV2.S (release titer) as the reference groups, with 90% power.

A target of approximately 240 participants (40 seronegative and 20 seropositive participants) per dose regimen in Groups 1, 3, 5, and 6 will be enrolled to further characterize the innate, pro-inflammatory and other relevant (eg, pro-thrombotic) responses to Ad26.COV2.S to better understand a possible risk to TTS events. This target may not be met due to the challenges of enrolling seronegative subjects into the study, so sub-study enrollment may stop at lower numbers.

Participants in the main study and sub-study (participants who are seronegative at enrollment or baseline) may be combined for the analysis.

[Table 7](#) shows how the power will be affected with 10%, 20%, 30%, 40%, 50% and 60% dropout due to various reasons (eg, lost to follow-up, participants with major protocol deviations with impact on immunogenicity, participants who become N-seropositive during the study or with a confirmed SARS-CoV-2 infection, and participants who received their vaccination outside the allowed window).

Table 7: Power Based on % of Drop Out

Regimen	sample size at enrollment per arm	group	% drop out since enrollment					
			10%	20%	30%	40%	50%	60%
9×10^{10} vp (sample size of main study and sub-study)	252 (212+40)	1	92.00%	88.60%	83.70%	76.80%	68.10%	57.20%
2.5×10^{10} vp (sample size of main study and sub-study)	252 (212+40)	5	92.00%	88.60%	83.70%	76.80%	68.10%	57.20%

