10.2. Appendix 2: Clinical Laboratory Tests

The following tests will be performed according to the Schedule of Activities (Section 1.4.1 and Section 1.4.2):

Laboratory Assessments	Parameters	Timepoints
Testing done locally/centrally	
 Urine pregnancy testing for participants of childbearing potential only Nasal swab sample and test for SARS-CoV-2 antibody Serology test for anti-SARS-CoV-2 N antibody Whole blood sample for platelet count which at some sites may be part of a complete blood count with differential Serum samples for humoral immunogenicity Serum/plasma samples for coagulation-related assays such as but not limited to: 
 Activated partial thromboplastin time Prothrombin time International normalized ratio Fibrinogen D-dimer Lupus anticoagulant Anti-cardiolipin antibody Beta-2 glycoprotein Heparin Induced Thrombocytopenia (HIT)/PF4 Ab, IgG·(HIT assay) Platelet activation assay (if HIT/PF4 is positive) Homocysteine ADAMTS13 Activity and Inhibitor Profile 	
 At screening and before each vaccination At screening and pre-vac 1 if the screening test was done more than 4 days before Day 1 At screening, At 28 days post-vac 1 and 14 days post-vac 2, and 24 weeks post-vac 2-. Testing may also be performed at 24 weeks post vac 2 from the humoral immunogenicity sample. Pre-vac 1, 28 days post-vac 1, pre-vac 2, and 14 days post-vac 2 with Ad26.COV2.S and as part of a (suspected) AESI investigation if applicable Pre-vac 1, 28 days post-vac 1, pre-vac 2, 14 days post-vac 2 and 24 weeks post-vac 2 Based on the clinical evaluation of the suspected AESI (eg, whether thrombocytopenia is observed with a thrombotic event), all or some of these tests may be conducted on the stored pre-vaccination sample (some of these tests will be conducted retrospectively) and on the samples obtained as part of the AESI investigation For all subjects from the main and sub study, at Pre-vac 1, 28 days post-vac 1, pre-vac 2, 14 days post-vac 2, all or some of these tests may be conducted on the samples (some of these tests will be conducted retrospectively)

Laboratory Assessments	Parameters	Timepoints

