2. STATISTICAL HYPOTHESES

The primary objective of this study is to demonstrate the NI, in terms of humoral immune response, of 1-dose and 2-doses of 9×10^{10} vp, 2.5×10^{10} vp, 7×10^{10} vp, 3.5×10^{10} vp, and 1.25×10^{10} vp Ad26.COV2.S versus 1-dose and 2-doses of 5×10^{10} vp Ad26.COV2.S (release titer).

Formal NI testing will be applied to demonstrate NI of 1-dose and 2-doses of 9×10^{10} vp, 2.5×10^{10} vp, 7×10^{10} vp, 3.5×10^{10} vp and 1.25×10^{10} vp Ad26.COV2.S versus 1-dose and 2-doses of 5×10^{10} vp Ad26.COV2.S (release titer), using a NI margin of 2/3 for the GMC ratios.

The following 2 sets of hypotheses (1 dose and 2 doses) will independently be tested sequentially:

Post-dose 1

- 1a) NI after 1-dose of Ad26.COVID-19 9×10^{10} vp versus 1-dose of Ad26.COVID-19 5×10^{10} vp (release titer)
- 1b) NI after 1-dose of Ad26.COVID-19 2.5×10^{10} vp versus 1-dose of Ad26.COVID-19 5×10^{10} vp (release titer)
- 1c) NI after 1-dose of Ad26.COVID-19 7×10^{10} vp versus 1-dose of Ad26.COVID-19 5×10^{10} vp (release titer)
- 1d) NI after 1-dose of Ad26.COVID-19 3.5×10^{10} vp versus 1-dose of Ad26.COVID-19 5×10^{10} vp (release titer)
- 1e) NI after 1-dose of Ad26.COVID-19 1.25×10^{10} vp versus 1-dose of Ad26.COVID-19 5×10^{10} vp (release titer)

In this set, NI will be demonstrated in terms of humoral immune response expressed by the GMCs of S-ELISA, 28 days post-dose 1, using a NI margin of 2/3 for the GMC ratio (GMC [9×10^{10} vp, 2.5×10^{10} vp, 7×10^{10} vp, 3.5×10^{10} vp, or 1.25×10^{10} vp]/GMC 5×10^{10} vp).

Post-dose 2

[figure not shown]
- 2a1) NI after 2-doses of Ad26.COVID-19 9×10^{10} vp versus 1-dose of Ad26.COVID-19 5×10^{10} vp (release titer)
- 2a2) NI after 2-doses of Ad26.COVID-19 9×10^{10} vp versus 2-doses of Ad26.COVID-19 5×10^{10} vp (release titer)
- 2b1) NI after 2-doses of Ad26.COVID-19 2.5×10^{10} vp versus 1-dose of Ad26.COVID-19 5×10^{10} vp (release titer)
- 2b2) NI after 2-doses of Ad26.COVID-19 2.5×10^{10} vp versus 2-doses of Ad26.COVID-19 5×10^{10} vp (release titer)
- 2c1) NI after 2-doses of Ad26.COVID-19 7×10^{10} vp versus 1-dose of Ad26.COVID-19 5×10^{10} vp (release titer)
- 2c2) NI after 2-doses of Ad26.COVID-19 7×10^{10} vp versus 2-doses of Ad26.COVID-19 5×10^{10} vp (release titer)
- 2d1) NI after 2-doses of Ad26.COVID-19 3.5×10^{10} vp versus 1-dose of Ad26.COVID-19 5×10^{10} vp (release titer)

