3. SAMPLE SIZE DETERMINATION

The number of participants chosen is to provide sufficient power for the non-inferiority comparisons.

The following assumptions were made in the sample size determinations:

Log transformed (\log_{10} scale) immune response data are normally distributed

A common standard deviation (SD): SD=0.5 (\log_{10} scale) of the immune response log transformed data

Non-inferiority margin = $\log_{10}(2/3) = -0.176$

Alpha = 0.0125 (1-sided) for 1- and 2-dose NI comparisons

- Alpha = 0.025 (one-sided). Using a Bonferroni correction, Type I error will be split equally over the 1-dose and 2-dose comparisons: 0.0125 (1-sided) for 1- and 2-dose NI comparisons

Power = 90%

Based on the above assumptions, and approximately a 10% dropout, a sample size of 225 participants per active vaccine group (see [Table 2](#)) is needed to detect non-inferiority of testing 1-dose and 2-doses of 9×10^{10} vp, 2.5×10^{10} vp, 7×10^{10} vp, 3.5×10^{10} vp, and 1.25×10^{10} vp Ad26.COV2.S as the test groups versus 1-dose and 2-doses of 5×10^{10} vp Ad26.COV2.S (release titer) as the reference groups, with 90% power (main study sample size assessment).

The originally intended NI population was comprised of participants from the main study who were SARS-CoV-2 seronegative at baseline and non-previously vaccinated. In addition, participants becoming infected with SARS-CoV-2 during the study are excluded from this population from the time of infection.

Participants were screened using a local SARS-CoV-2 serology test to ensure only participants who were seronegative at baseline were enrolled in the main study. However, a preliminary blinded evaluation of central N-serology results in main study participants at Day 29 and Day 71 showed that overall, 27% and 38% of participants, respectively, were N-serology positive at these time points. The higher-than-expected N-serology positive status at Day 29 and Day 71 indicated that participants became infected during the study and/or local serology tests were not sufficiently sensitive, affecting the power of the study.

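### The non-inferiority models adjust for nothing beyond yes/no serostatus, and the stated interval carries no covariate at all, so modest precision is left unused in a trial short of power

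*SAP*

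**What the plan says.** SAP 5.5.3.1 offers two confirmatory models for log10 S-ELISA. In Scenario 1, on the baseline-seronegative NI set, "A linear regression analysis with only one main effect (dose level) will be fitted". In Scenario 2, on the PPI set, the model has "dose level and SARS-CoV-2 serostatus at baseline as the independent variables". Scenario 2 applies if more than 40% of evaluable data points are lost from the NI set at Day 29 (SAP 4.2).

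The same section then builds the decision interval from the difference of two raw group means, a variance pooled over those two groups, and a t quantile. If the variances differ, a Satterthwaite version is used. Neither version has a covariate term.

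The candidate covariates are already in hand. SAP 5.2.1 summarises age, sex and BMI for the FAS, and SAP 5.5.3 states that "Key immunogenicity subgroup analyses will also be performed by age group, sex, BMI, race, ethnicity, and serostatus at baseline". Protocol Appendix 2 schedules the humoral serum samples at "Pre-vac 1, 28 days post-vac 1, pre-vac 2, 14 days post-vac 2 and 24 weeks post-vac 2", and Protocol 9.2.1 says that samples from all participants are run in S-ELISA. Protocol 6.3 describes randomisation in permuted blocks and names no stratification factor.

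SAP 3 and 4.2 report central N-serology positivity of 27% at Day 29 and 38% at Day 71 and say that this affects power.

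**The concern.** When power is short, adjusting for baseline variables that predict the response is one of the few remedies that needs no further data. The sponsor pooled the main and sub study, reordered the hypotheses and added a fallback population, but left the models bare. In Scenario 2, one yes/no term treats weakly and strongly primed seropositives alike although their Day 1 titre is available.

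Unexplained variance widens every interval. Testing within each family is sequential, so a comparison missed for lack of precision blocks the later hypotheses in that family.

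The text also has a structural gap: Scenario 2 specifies a regression with serostatus, but the interval used to declare non-inferiority is written without it.

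**Working it through.** **Inputs from the documents.** Margin: "using a NI margin of 2/3 for the GMC ratios", so log10(1.5) = 0.1761. Error rate: "Alpha = 0.0125 (1-sided) for 1- and 2-dose NI comparisons". Variability: "A common standard deviation (SD): SD=0.5" on the log10 scale. Design size, Protocol 9.2: "assuming approximately a 10.2% dropout, a sample size of 225 participants per active vaccine group". Enrolled numbers per arm in SAP Table 4: 265 (doses shared with the sub study) and 225 (main study only). True GMC ratio taken as 1 throughout.

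**Step 1: reproduce the plan's sample size.** n = 2 × SD² × (z0.9875 + z0.90)² / margin² = 2 × 0.25 × (2.2414 + 1.2816)² / 0.1761² = 200.1, so 201 evaluable. The noncentral t gives 202 (90.1% power), and 202 / 0.898 = 224.9, so 225. The plan's figure reproduces.

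**Step 2: reproduce SAP Table 4 at 40% loss.** With 265 × 0.6 = 159 per arm, SE = 0.5 × √(2/159) = 0.0561 and 0.1761 / 0.0561 = 3.14. Noncentral t power is 81.2% (table: 81%). With 225 × 0.6 = 135 per arm it is 73.8% (table: 74%). The reference arm is itself a 265 arm, so the 7×10^10 and 3.5×10^10 vp comparisons are 135 v 159, with power 77.5%.

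**Step 3: Scenario 1 with age, sex and BMI.** Residual SD = 0.5 × √(1 − R²). The documents give no R², so the range is assumed.

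| R² | Residual SD | 40% loss, 265 v 265 | 40% loss, 225 v 265 | 27% loss, 265 v 265 |
|---|---|---|---|---|
| 0 | 0.500 | 81.2% | 77.5% | 88.7% |
| 0.01 | 0.4975 | 81.7% | 77.9% | 89.0% |
| 0.03 | 0.492 | 82.5% | 78.8% | 89.7% |
| 0.08 | 0.480 | 84.6% | 81.1% | 91.3% |

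Forty per cent is the largest Day 29 loss at which Scenario 1 still applies; 27% is the Day 29 N-positivity alone, before other losses.

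Day 1 S-ELISA adds nothing here. Seronegative requires a negative baseline S-ELISA (SAP 5.1.5), positive means above LLOQ (SAP 6.1.4), and values below LLOQ are set to LLOQ/2 for geometric means (SAP 6.1.2). The covariate is therefore essentially constant in the NI set.

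**Step 4: Scenario 2 with Day 1 titre among seropositives.** Let p be the seropositive fraction and ρ the correlation of Day 1 with post-dose log10 titre in that stratum. Average residual variance = (1 − p) × 0.25 + p × SDpos² × (1 − ρ²). Assumed: SDpos = 0.5, ρ = 0.4 to 0.7, 200 evaluable per arm. Without the titre the variance is 0.25 and power is 89.8%.

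- p = 10%: variance 0.225 + 0.025 × 0.84 = 0.2460 down to 0.225 + 0.025 × 0.51 = 0.2378. Power 90.3% to 91.3%.
- p = 25%: variance 0.1875 + 0.0625 × 0.84 = 0.2400 down to 0.1875 + 0.0625 × 0.51 = 0.2194. Power 91.0% to 93.4%.

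**Step 5: the whole post-dose 1 sequence.** Simulation of the five steps in SAP order at 40% loss, all true ratios 1 and a shared reference arm, gives a chance of passing every step of 50.6% unadjusted, 54.3% at R² = 0.05 and 58.4% at R² = 0.10.

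**The case against.** The strongest reply is that this is a choice about efficiency, not an error. No stratification is stated, so the unadjusted comparison is valid and alpha is unaffected; chance imbalance is already covered by the interval. That stands in full. A reader might infer that leaving the covariates out biases the contrast or inflates error, and the documents do not support this.

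The second reply is that the size is unknown. Enrolment is limited to healthy adults of 18 to 55 years with BMI below 35 kg/m² (Protocol 5.1), which narrows two of the three covariates, and no R² or correlation is given anywhere. That also stands: the gain could be under one point. Listing age, sex and BMI as subgroups does not show that the sponsor regards them as predictors of response.

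Other tempting readings go too far. Day 1 S-ELISA is not a lost covariate in the base case, because it is essentially constant there. A miss does not stop a whole family unless it is the first test (1a or 2a1); earlier successes stand. Nor do the figures show that over a third of participants leave the NI set after randomisation. The Day 29 figure is 27%, and the SAP attributes positivity to infection during the study and/or insensitive local tests, the latter being a pre-vaccination attribute.

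Finally, the documents do respond to the power loss by other means. That is true, but covariate adjustment is compatible with all of them.

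**Conclusion.** The point holds as a recommended improvement. Neither confirmatory model uses age, sex or BMI, Scenario 2 does not use the Day 1 titre, and the stated interval does not match Scenario 2's own regression. The first two matters cost precision; the third is an inconsistency to settle whatever is decided about covariates.

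Under the assumed R² of 3-8%, the Scenario 1 gain at 40% loss is 1.3 to 3.4 points (82.5 − 81.2 and 84.6 − 81.2) for 265 v 265, and 1.3 to 3.6 points (78.8 − 77.5 and 81.1 − 77.5) for 225 v 265. In Scenario 2, under the stated assumptions, it is 0.5 to 1.5 points at 10% seropositive and 1.2 to 3.6 points at 25%. The R², correlations, seropositive fractions, stratum SD and 200 per arm in Scenario 2 are all assumptions. The design inputs and the unadjusted Scenario 1 power are the plan's own and reproduce.

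**What to change.** Before unblinding, amend SAP 5.5.3.1 as follows:

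- Add continuous age, sex and continuous BMI to both models.
- In Scenario 2 only, add log10 Day 1 S-ELISA within the baseline-seropositive stratum, set to a constant for seronegatives. State the convention for values below LLOQ.
- Take the GMC ratio and its two-sided 97.5% CI from the fitted model, replacing the two-sample formula, and say what happens to the equal-variance test and Satterthwaite fallback. Adding terms to the regression without this step would leave the decision rule unchanged.
- Give a simple rule for missing covariates, such as mean imputation.
- Report the current SAP model as supportive.

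The cost is a rewrite of the interval text and a few degrees of freedom out of several hundred; no new data, visits or participants are needed. Timing matters because Protocol 9.5 and SAP 7 allow the sponsor to be unblinded. If treatment-level data have already been seen, the adjusted model should be supportive only.

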Per amendment 5, an additional enrollment of adult participants 18 to 55 years, inclusive, will enroll into the sub study, into group 1, 3, 5 and 6 to further characterize the innate, pro-inflammatory and other relevant (e.g., pro-thrombotic) response to the Ad26.COV2.S to better understand a possible risk to TTS events. Participants will receive Ad26.COV2.S administered IM.

A target of approximately 240 participants (approximately 40 seronegative and approximately 20 seropositive participants per dose regimen) will be enrolled in the sub study and will receive a 2-dose vaccination regimen at either 9×10^{10} vp, 5×10^{10} vp, 2.5×10^{10} vp or 1.25×10^{10} vp.

Table 3 : Schematic Overview of Study Design and Groups for the Sub Study

Group	N seronegative	N seropositive	Day 1 Vaccination 1	Day 57 Vaccination 2
1	N ~ 40	N ~ 20	Ad26.COV2.S 9×10^{10} vp	Ad26.COV2.S 9×10^{10} vp
3	N ~ 40	N ~ 20	Ad26.COV2.S 5×10^{10} vp	Ad26.COV2.S 5×10^{10} vp
5	N ~ 40	N ~ 20	Ad26.COV2.S 2.5×10^{10} vp	Ad26.COV2.S 2.5×10^{10} vp
6	N ~ 40	N ~ 20	Ad26.COV2.S 1.25×10^{10} vp	Ad26.COV2.S 1.25×10^{10} vp

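### SAP 5.5.3.1 gives two incompatible rules for the Scenario 2 primary analysis: a serostatus-adjusted regression and a printed two-sample t bound with no serostatus term

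*SAP*

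**What the plan says.** SAP 4.2 allows participants who are centrally seropositive at baseline into the non-inferiority assessment on the condition that serostatus is an independent variable. This is Scenario 2, which uses the PPI set and is triggered by more than 40% loss in the NI set at Day 29. SAP 5.5.3.1 names the model: "A linear regression analysis with two main effects (dose level and SARS-CoV-2 serostatus at baseline) will be fitted".

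The same section then sets out how non-inferiority is assessed. It builds an interval for the "difference in means based on the sampling distribution of two independent normal distributions with variances that are unknown but assumed equal". The formula uses raw arm means, a two-arm pooled SD and n_g + n_r − 2 degrees of freedom. The criterion covers all dose-level "comparisons (post-dose 1 and post-dose 2), NI will be demonstrated if" the lower bound exceeds 2/3. If variances differ, the fallback is a Satterthwaite two-sample t. Serostatus appears nowhere in this rule, and the rule is not confined to Scenario 1.

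On the sub-study, SAP 1.3 says "approximately 40 seronegative and approximately 20 seropositive participants per dose regimen) will be enrolled in the sub study", in groups 1, 3, 5 and 6 only. Group 3 is the 5×10^10 reference. Groups 2 (7×10^10) and 4 (3.5×10^10) receive none of these participants.

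**The concern.** A confirmatory decision rule has to be unique. Here a programmer could follow the regression or the printed formula, and the two can give opposite answers on the same data.

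Under the printed formula in Scenario 2, the reference arm holds a larger share of previously infected people than the 7 and 3.5×10^10 arms. If those people respond higher, a test dose equal to the reference looks worse than it is. Between-stratum variance also stays in the error term of every comparison. In the order listed in SAP 2 and 5.5.3, 7×10^10 comes before 3.5 and 1.25×10^10. A false failure at 1c, 2c1 or 2c2 would therefore stop testing of two doses meant to inform product expiry.

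**Working it through.** **Reproducing the plan.** SAP 3 gives "A common standard deviation (SD): SD=0.5" on the log10 scale, a margin of log10(2/3) = −0.176 and "Alpha = 0.0125 (1-sided) for 1- and 2-dose NI comparisons". With a true difference of 0 (not listed, but it reproduces the plan), noncentral-t power reaches 90% at 202 per arm. With the protocol's 10.2% dropout, 202/0.898 = 224.9, so 225. For SAP Table 4 the same method gives 90.2/86.2/80.8/73.8/65.0/54.2% at 225 per arm and 94.5/91.5/87.3/81.2/73.0/62.1% at 265, which agrees with the table.

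**Scenario 2 case.** Arms at enrolment: test 225; reference 225 + 40 + 20 = 285. Assumptions:
- 80% retained, giving 180 and 228.
- p = 27% centrally seropositive at baseline among those locally seronegative. This borrows the SAP's Day 29 N-positivity, which mixes baseline positives with new infections.
- All 20 sub-study seropositives are centrally positive.
- SD 0.5 within serostatus stratum, true ratio 1, one-sided alpha 0.0125.
- Serostatus effect d of 0.2 to 1.0 log10, since the documents give none.

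Trigger check: the NI set keeps 0.80 × 0.73 = 58.4%, a 42% loss, so Scenario 2 applies.

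**Imbalance.** p_ref = (265 × 0.27 + 20)/285 = 0.321, against 0.27 in the test arm: 5.1 points.

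**Printed rule at d = 0.5.**
- Bias = −0.0512 × 0.5 = −0.0256 log10, an expected ratio of 0.943; 0.0256/0.176 = 15% of the margin.
- Variance per arm = 0.25 + p(1−p)d²: 0.299 and 0.304, pooled 0.302.
- SE = √[0.302 × (1/180 + 1/228)] = 0.0548.
- Noncentrality = (0.1761 − 0.0256)/0.0548 = 2.75, giving power of 69%.

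**Regression.** Stratum information 1/(1/n_test + 1/n_ref) is 29.2 for seropositives (48.6 and 73.2 people) and 71.1 for seronegatives (131.4 and 154.8), total 100.3. SE = √(0.25/100.3) = 0.0499. Noncentrality = 0.1761/0.0499 = 3.53, giving power of 90% whatever d is.

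| d (log10) | Expected raw ratio, 7 and 3.5 | Power 7 and 3.5: printed / regression | Power 9, 2.5 and 1.25: printed / regression |
|---|---|---|---|
| 0.2 | 0.977 | 85% / 90% | 93% / 93% |
| 0.3 | 0.965 | 80% / 90% | 92% / 93% |
| 0.5 | 0.943 | 69% / 90% | 88% / 93% |
| 1.0 | 0.889 | 34% / 90% | 69% / 93% |

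A 4,000-run simulation agrees: 68.8% against 90.4% at d = 0.5, and 33.8% against 90.2% at d = 1.0. At d = 1.0, variance inflation alone takes 7 and 3.5×10^10 from 90% to 64%; bias accounts for the rest.

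**Quantile.** The formula uses t(1−α/2) with α = 0.0125, which is one-sided 0.00625 and a 98.75% two-sided interval. The section elsewhere specifies 97.5% two-sided. Taken literally, the printed rule gives about 73%, 59% and 25% at d = 0.3, 0.5 and 1.0, and the regression 85%. The table uses the intended 0.0125.

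**The case against.** The strongest reply is that the SAP does prespecify adjustment. SAP 4.2 makes modelling of serostatus the condition for using seropositives, and 5.5.3.1 names the model. The formula may be generic two-arm text; it even refers to an equation number that does not appear. That stands. A reader might infer that the plan leaves serostatus out of the Scenario 2 decision on purpose, and the documents do not support this. What remains is that the printed criterion is worded for all comparisons and no sentence ties it to the model.

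A reader might also infer that a large power loss is established. It is not, because it depends on an effect size the documents do not give: at 0.2 log10 the loss is about 5 points. Reading 0.5 as the overall SD, not the within-stratum SD, raises the printed rule's power to about 78% at d = 0.5 and 60% at d = 1.0.

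Nor does every plausible case reach Scenario 2. With 80% retained and 20% seropositive, 0.80 × 0.80 = 64% remain, a 36% loss, and Scenario 1 applies. Of nine combinations (70/80/90% retained; 10/20/27% seropositive), three pass 40%.

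Two further inferences fail. The power loss is not confined to 7 and 3.5×10^10; only the bias is. And if seropositives respond higher, the bias runs against the test dose, so false non-inferiority claims do not become more likely.

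**Conclusion.** The contradiction is on the page and should be resolved: one section gives two rules for the Scenario 2 primary analysis, and one of them breaks the SAP's own condition for including seropositives. The harm is conditional on three things: Scenario 2 being triggered, the printed formula being the one applied, and seropositives responding higher.

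Given those, the expected ratio for 7 and 3.5×10^10 falls to between 0.98 and 0.89 when the truth is 1, and power falls from 90% to between 85% and 34% for effects of 0.2 to 1.0 log10. The other three doses lose precision only, from 93% to as low as 69%. The consequence is a false failure that can end the sequence early, not a false success.

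**What to change.** In SAP 5.5.3.1:

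1. State that in Scenario 2 non-inferiority is concluded if the lower limit of the two-sided 97.5% CI for the back-transformed, serostatus-adjusted dose contrast against 5×10^10, taken from the fitted regression with its own residual variance and degrees of freedom, exceeds 2/3.
2. For 2a1 to 2e1, which compare the test arm at Day 71 with the reference at Day 29, a single-timepoint regression does not supply the contrast. State that the same serostatus-adjusted model is fitted to those two sets of samples.
3. Limit the two-sample formula and its Satterthwaite fallback to Scenario 1.
4. Write the quantile as t(1 − 0.025/2), so that the interval is the stated 97.5% two-sided one.

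The cost is SAP wording and a model contrast per comparison. No new data are needed. The choice should be fixed before results by dose group are seen.
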